5.3 Concomitant Interventions

Allowed, required, and prohibited interventions (e.g., medications) will depend upon the study interventions and outcomes.

This section should be consistent with the medications and interventions restrictions in the inclusion/exclusion criteria.

5.3.1 Allowed Interventions

- Patients who develop an unexpected allergic reaction to either local or general anesthesia can be treated with antihistamines, epinephrine, and steroids according to standard hospital protocol.
- Patients who experience scrotal swelling postoperatively can be treated with ice packs and may undergo ultrasonography if there is suspicion for testicular injury. If testicular injury is found, urology service will be consulted for management.
- Patients who experience urinary retention (>200 mL of urine on bladder scan with inability to void) will undergo in and out catheterization followed by observation for up to 4 hours after. If they still demonstrate urinary retention at that time, they will be admitted to the hospital with placement of a Foley catheter and subsequent evaluation by urology.
- Patients with wound infections postoperatively will be managed by opening of the incision and administration of antibiotics, with or without readmission to the hospital.
- Patients who demonstrate malignant hyperthermia in response to general anesthesia will be treated with dantrolene and admission to the ICU for monitoring and resuscitation.
- Administration of IV fluids and IV or oral pain medications in the recovery area after surgery is permissible at the discretion of the attending anesthesiologist.

List all drugs and/or treatments/interventions that are allowed, including rescue medications, while on study.

5.3.2 Required Interventions

- All patients will be provided postoperative pain control consisting of 20 tablets of acetaminophen 300 mg / hydrocodone 5 mg, accompanied by 20 tablets of 10 mg bisacodyl to address constipation from opioids and anesthesia.

For example, if in weight loss study, vitamin pills may also be required.

5.3.3 Prohibited Interventions

- N/A

Include classes of medications, devices, etc. from the exclusion criteria (section 4.2) if they are also prohibited while the participant is on study. If necessary, provide a list of prohibited medications in appendix.

5.4 Adherence Assessment

We will review all operative and anesthesia records for cases of enrolled patients to verify the type of anesthesia that is administered and whether patients who start the operation under local anesthesia undergo a conversion to general anesthesia. Research assistants will also review cases with attending surgeons at the end of each operative day to identify any deviations from protocol. Any deviation from treatment assignment will then be recorded in the research record.

Adherence to a study regimen is generally defined as the extent to which participants take medications or comply with other study requirements as prescribed by the investigators. Define adherence (e.g., at least 80% of treatment intervention pills taken, 85% of exercise sessions attended). Provide details as to how adherence to study intervention will be assessed (e.g., pill counts, electronic monitoring devices, attendance at counseling sessions) and in the section on Data Analyses (Section 9.5), describe how this information will be incorporated into the analysis of the study results.

6 STUDY PROCEDURES

The Schedule of Evaluations in section 6.1 should include all study evaluations. Use an 'X' in a cell to indicate that a particular evaluation is to be performed at a particular study visit. The evaluations listed and their order in the table are only examples. The evaluations should reflect the protocol and should be arranged for clearest presentation. Additional columns may be needed to specify evaluations at intervention failure, at early discontinuation of study interventions, or at other special time points that require a different set of evaluations. In complicated studies with multiple study steps or multiple randomization points, it may be useful to include in the table the time of each step/randomization and the time that study intervention is given to the participant.

6.1 Schedule of Evaluations

Study evaluations are outlined in **Table 1** (next page). Laboratory tests are limited to those obtained routinely as part of the preoperative evaluation so no additional labs/blood draws will be required as part of this study.

Assessment	Screening: Visit-1 (Initial Surgery Clinic Visit)	Baseline, Enrollment, Randomization: Visit 1 (Day 0: Initial Clinic Visit)	Treatment Visit 2 (During Surgery)	Treatment Visit 3 (After Surgery & Before Same Day Discharge)	Treatment Visit 4 (48 Hours After Surgery)	Treatment Visit 5 (2-Week Postoperative Visit)	Follow-Up: Final Visit (6- Month Postoperative Visit)
Informed Consent Form	X						
Demographics	X						
Medical & Surgical History	X						
General Physical Examination	X						
Current Medications	X						
Inclusion/Exclusion Criteria	X						
Blood Chemistries		X					
Hematology		X					
Urine Analysis		X					
Vital Signs		X	X	X		X	
Enrollment/Randomization		X					
Physical Function Assessment: Katz Index		X			X	X	X
Delirium & Cognitive Assessment: (1) Confusion Assessment Method short form, (2) Montreal Cognitive Assessment (5 minute version), (3) Trail Making Tests Parts A & B.		X		X	X	X	X
Frailty Assessment: Fatigue, Resistance, Ambulation, Illness and Loss of Weight Scale		X					
Pain Assessment: Visual Analog		X		X	X	X	X
Quality of Life: Carolinas Comfort Scale		X			X	X	X

Total Operating Room Time			X				
Time for Surgery			X				
Time in Post-Anesthesia Recovery Room				X			
Time in Step-Down Recovery Room				X			
Urinary Function/Unplanned Catheterization				X			
Unplanned Admission				X			
Adverse Events			X	X	X	X	X

6.2 Description of Evaluations

Descriptions for the Schedule of Evaluations define what is to be done at each study period and include special considerations or instructions for evaluations.

This section should include definitions of the column headings in the Schedule of Evaluations and any special instructions.

For studies collecting biological samples, describe the process for obtaining, processing and storing the samples. Include details on handling, preserving and shipping the specimens (e.g., required temperatures, location of storage, labeling).

6.2.1 Screening Evaluation and consent

These evaluations occur to determine if the candidate is eligible for the study.

Screening

Initial screening procedures will occur at least 24 hours prior to surgery and will be completed by research assistants. Screening procedures will determine whether the patient is the appropriate age and has a unilateral non-incarcerated inguinal hernia that has not previously been surgically repaired. This information will be obtained by reviewing the consult request, consult note, and prior medical records. The remainder of the screening (for patients found to be in the appropriate range, having unilateral and non-recurrent and non-incarcerated inguinal hernias) will occur at the time of the clinic visit when the participant is evaluated by the general surgery team. If patients are deemed to be candidates for surgery by the attending surgeon in clinic, then research assistants will obtain additional information on eligibility from the surgical team and approach potential participants as outlined below. All information necessary to determine eligibility will be available from the standard history and physical obtained by the surgical team as part of routine care for hernia patients. Research assistants will verify the information prior to enrollment.

Procedures

- Demographics: we will determine the participant's age, as this is one of our critical inclusion criteria.
- Medical & surgical history: we will verify that the patient has not had prior hernia surgery on the affected side and that he/she has no disqualifying medical conditions that would prevent the use of either local or general anesthesia.
- General physical examination: we will verify that the clinical team detected the presence of an inguinal hernia that is not incarcerated and does not require emergency surgery (strangulation or peritonitis).
- Current medications: we will verify the absence of medications that might cause adverse reactions with either general or local anesthesia.

Decision points regarding eligibility:

- Demographics: if patient age is <65 years old, they will not be eligible
- Medical & surgical history:
 - if the patient had prior hernia surgery on the affected side, then they will not be eligible
 - if the patient has a known allergy to local anesthesia or general anesthesia (or a reaction such as malignant hyperthermia), then they will not be eligible
 - If the patient has medical conditions that are relative or absolute contraindications to the use of general anesthesia or to surgery (heart failure with ejection fraction <20%, chronic obstructive pulmonary disease with a significant oxygen requirement, Child's C cirrhosis, any terminal disease with life expectancy < 6 months), then they will not be eligible
 - If the patient is taking any medication that might adversely interact with anesthesia and cannot be discontinued, then they will not be eligible

Specify allowable range of time prior to study entry during which all screening evaluations to determine eligibility must be completed. List and briefly describe all screening evaluations in bulleted format.

Include only those evaluations that are necessary to assess whether an individual meets enrollment criteria. Discuss the sequence of events that should occur during screening and the decision points regarding eligibility. List the time frame prior to enrollment within which screening tests and evaluations must be done. For example, DXA must be measured within 30 days of study enrollment.

Consenting Procedure

Potential participants will be identified by study research assistants 24-48 hours prior to their initial visit to the surgeon to discuss whether they will undergo hernia repair. We have obtained a waiver of informed consent from the IRB to review upcoming clinic records for this purpose. Once the consulting surgeon has determined that the patient needs surgery and the patient agrees to proceed with the operation, our research assistants will approach the patient to obtain consent for screening and study procedures (as a single consent form). At that time, the research assistant will explain the study purpose and discuss the potential risks/benefits of local anesthesia and general anesthesia, including the possibility of allergic reactions, heart attacks, stroke, blood clots, low blood pressure, pain, nausea, vomiting, and cognitive changes.

Patients who are not enrolled at the initial clinic visit may still be enrolled at subsequent preoperative visits as long as they occur at least 24 hours prior to surgery.

We will maintain records of informed consent as follows: a hard copy will be given to the patient and also stored in a secured filing cabinet in the PI's research office. We will also scan a copy

into the electronic medical record and store another scanned copy on our secure electronic research server. All informed consent forms will have a date and version number on the top right corner of all pages. The consent will include permission to contact participants by phone if needed to discuss any changes to the study protocol or other issues that occur during the trial.

Before any screening procedure is performed, informed consent must be obtained. Indicate whether there will be two consenting processes or a single informed consent form that describes both the screening and study procedures.

State which study staff will conduct the consent process and how it will be implemented.

Describe individual's education and informed consent process; any plan for review of consent document in case changes may be required; and how documentation of signed consent will be maintained by the study.

6.2.2 Enrollment, Baseline, and/or Randomization

Enrollment

Enrollment is defined as the date that screening criteria are met and the individual agrees to participate and be randomized to either local or general anesthesia. The enrollment date will be recorded on the participant's case report form.

The act of enrolling a study participant should be defined. Since informed consent must be obtained if screening procedures are not a part of routine care, some studies use two informed consents: one for screening and one for enrollment. In this case the enrollment date is day the individual has met all the screening criteria and signs the second informed consent form.

Some studies utilize a single informed consent form that describes both screening and study procedures. In these studies enrollment is defined as the randomization date or as the date all of the screening criteria are met and the individual agrees to participate

In any case the enrollment date should be defined and recorded on a case report form along with the allowable window between screening and randomization.

Baseline Assessments

In addition to the information obtained as part of the screening evaluation, our research assistants will also obtain the following information:

- Laboratory evaluations: as part of the routine preoperative evaluation at our hospital sites, the following labs are obtained: blood chemistry, hematology/complete blood count, urine analysis. None of these labs will be ordered as part of our study, but we will record the information from this

routine screening in each patient's data file.

- Physical function assessment: we will administer the 6-item Katz index to measure independence in activities of daily living
- Delirium and cognitive assessment: we will administer a battery of tests to assess (1) cognitive function (overall and particular domains including processing, visual scanning, attention, mental set-shifting, executive function, and verbal memory) and (2) delirium risk
 - Confusion Assessment Method (short form)
 - Montreal Cognitive Assessment (5 minute version)
 - Trail Making Tests Parts A and B
- Frailty assessment: we will administer the 5-item Fatigue, Resistance, Ambulation, Illness, and Loss of Weight Scale to obtain a global measurement of frailty.
- Pain assessment: we will administer a 10-point visual analog scale to quantify pain levels related to the hernia
- Quality of life: we will use the 8-item Carolinas Comfort Scale to assess hernia-related quality of life
- Presence of symptoms indicating urinary retention (if not already identified by clinical team during history and physical)

For participants who have successfully been screened for eligibility and are enrolled into the study, baseline assessments are performed against which to measure the study outcome. They also ensure that the groups are balanced with respect to baseline characteristics. For example if the study hypothesis is “dietary intervention and exercise will reduce body weight by X% within one year”, body weight will be assessed and documented.

List and briefly describe all baseline evaluations in a bulleted format.

Randomization

As outlined in section 4.4, randomization will occur immediately after screening and baseline assessment because the anesthesia team will need to be aware of the anesthetic plan prior to surgery, and the anesthesia team sees patients in their clinic after the surgical visit is complete. The study intervention (use of local or general anesthesia) will occur at the time of surgery, typically 4-6 weeks after the surgical clinic visit occurs and randomization is completed.

Randomization must precede intervention administration in a randomization study. Specify time window for (a) randomization relative to completion of screening and baseline and (b) initiation of study intervention relative to randomization.

6.2.3 Follow-up Visits

- Visit 2 (During Surgery)
 - The second set of assessments will occur during the normal course of clinical care for inguinal hernias (this does not represent an additional study visit on top of the usual care). During the surgery, the

anesthesiologist automatically records data on the below information as part of the routine anesthesia record.

- Vital signs: maximum, minimum, and median values for systolic and diastolic blood pressure and heart rate
 - Total operating room time: the difference between the time the patient enters the operating room and the time the patient leaves the operating room
 - Time for surgery: the time from the start of the operation (skin incision) and the end of the operation (skin closure)
 - Adverse events, serious adverse events, and intraoperative complications
 - Volume of fluids administered
 - Minimum alveolar concentration of volatile anesthetic
 - Dose of local anesthesia used
- Visit 3 (After Surgery & Before Same Day Discharge)
 - Inguinal hernia repair is typically an outpatient procedure where the patient is observed for several hours to ensure that there are no immediate complications of surgery or anesthesia and that patients are able to ambulate, tolerate oral intake, and manage basic self-care with assistance from family or other caregivers. From the time the patient leaves the operating room until the time the patient leaves the hospital, we will assess the following:
 - Vital signs: We will record any episodes of hypotension (mean arterial pressure <60) or hypertension (systolic blood pressure >180 or diastolic > 110), fever (temperature >101.6 F), tachycardia (heart rate >120), or poor oxygenation (oxygen saturation on pulse oximetry <85%). This information will be obtained from the post-anesthesia care unit and stepdown unit records.
 - Delirium and cognitive assessment: we will administer a battery of tests to assess (1) cognitive function (overall and particular domains including processing, visual scanning, attention, mental set-shifting, executive function, and verbal memory) and (2) delirium risk
 - Confusion Assessment Method (short form)
 - Montreal Cognitive Assessment (5-minute version)
 - Trail Making Tests Parts A and B
 - Time in post-anesthesia care unit: after surgery, all patients who had their operations performed under general anesthesia are observed in a unit with a nurse:patient ratio of $\leq 2:1$, similar to intensive care units. This level of nursing care is required to quickly detect immediate complications of anesthesia, including respiratory failure and hypotension. Our research assistants will use the nursing records to determine what time the patient entered the unit and what time they were transferred to the next phase in care: the step-down unit. Patients having

surgery under local anesthesia are sent directly from the operating room to the step-down unit.

- Time in step-down unit: Once general anesthesia patients meet criteria in the post-anesthesia care unit (awake, normal respiratory drive and blood pressure), they are transferred to the step-down unit. All local anesthesia patients are transferred directly to the step-down unit once their operation is complete. In this unit, patients are provided food and liquids to test their ability to tolerate oral intake. Patients also are asked to ambulate and void to ensure that they are capable of self-care and have not developed urinary retention. Our research assistants will use nursing records to identify the time of entry and departure from the step-down unit.
 - Urinary function/unplanned catheterization: research assistants will review nursing notes to determine whether patients were able to void or whether they required assistance. Our standard clinical protocol is that if patients have not urinated by 4 hours after surgery, they will undergo a bladder scan. If >200cc of urine is found in the bladder, the patients undergo in-and-out catheterization and are observed until they void again. If still unable to void, the patient has a foley catheter placed, is started on medication for prostatic hypertrophy, and arrangements are made with the urology service to undergo outpatient voiding studies and removal of the catheter within 1-2 weeks.
 - Unplanned admission: since most inguinal hernia surgeries are outpatient procedures, our nursing assistants will check the medical record the day after surgery to see if the patient was able to leave or was admitted. If admitted, we will contact the team to determine the reason for admission.
 - Adverse events and serious adverse events
- Visit 4 (48 Hours After Surgery)
 - Research assistants will contact the patient by phone to complete assessments. This may be completed at any time from 48 hours to 1 week after surgery.
 - Physical function assessment: we will administer the 6-item Katz index to measure independence in activities of daily living
 - Delirium and cognitive assessment: we will administer a battery of tests to assess (1) cognitive function (overall and particular domains including processing, visual scanning, attention, mental set-shifting, executive function, and verbal memory) and (2) delirium risk
 - Confusion Assessment Method (short form)
 - Montreal Cognitive Assessment (5-minute version)
 - Trail Making Tests Parts A and B
 - Pain assessment: we will administer a 10-point visual analog scale to quantify pain levels related to the hernia
 - Quality of life: we will use the 8-item Carolinas Comfort Scale to

- assess hernia-related quality of life
- Adverse events
- Visit 5 (2-Week Postoperative Visit)
 - Our standard clinical practice is to bring patients back to surgery clinic within 2-4 weeks of surgery to assess recovery and evaluate the incision. This assessment can take place any time in that 2-4 week postoperative period.
 - Vital signs
 - Physical function assessment: we will administer the 6-item Katz index to measure independence in activities of daily living
 - Delirium and cognitive assessment: we will administer a battery of tests to assess (1) cognitive function (overall and particular domains including processing, visual scanning, attention, mental set-shifting, executive function, and verbal memory) and (2) delirium risk
 - Confusion Assessment Method (short form)
 - Montreal Cognitive Assessment (5-minute version)
 - Trail Making Tests Parts A and B
 - Pain assessment: we will administer a 10-point visual analog scale to quantify pain levels related to the hernia
 - Quality of life: we will use the 8-item Carolinas Comfort Scale to assess hernia-related quality of life
 - Adverse events

Indicate treatment and follow-up visit assessments for each visit. List all measurements and procedures in bulleted format.

Include allowable time window in which evaluations may take place, e.g., study visits must be performed on the weeks indicated in the Schedule of Evaluations $\pm X$ days. The evaluation time window should be as narrow as technically feasible.

For example:

- Visit 3:
 - *Vital Signs*
 - *Treatment Administration Form*
 - *Concomitant Medications*
 - *Adverse Events*

- Visit 6:
 - *General Physical Examination*
 - *Vital Signs*
 - *Treatment Administration Form*
 - *Concomitant Medication*
 - *Adverse Events*

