7.1.2 Definition of serious adverse events (SAE)

A SAE is any event that results in death, a life-threatening adverse event, inpatient hospitalization or prolongation of existing hospitalization, a persistent or significant incapacity or substantial disruption of the ability to conduct normal life functions, or a congenital anomaly/birth defect. Important medical events that may not result in death, be life-threatening, or require hospitalization may be considered serious when appropriate medical judgement indicates they may jeopardize the patient and may require medical or surgical interventions to prevent outcomes listed in this definition.

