7.1.5 SAE/AE occurring only with general anesthesia

- Malignant hyperthermia: some patients can have a severe reaction to general anesthesia that includes a substantial increase in body temperature (sometimes as

high as 113° F) and rigid/painful muscles. If this occurs during surgery, the operation will immediately be stopped and patients will receive intravenous dantrolene. Patients will be admitted to the intensive care unit where they will continue to receive care including cooling blankets and fluids, oxygen, correction of electrolyte abnormalities, and standard medications to manage tachycardia and hypotension. We will also monitor kidney function and changes in creatinine kinase. The occurrence of this complication will not change the study intervention regimen or the schedule of participant assessments.

- Urinary retention: per our standard hospital protocol, if patients are unable to urinate by four hours after surgery, we will perform a bladder scan. If >200 mL of urine is seen, the patient will receive an in-and-out catheterization followed by observation for up to an additional four hours. If the patient is still unable to urinate, they will have a Foley catheter placed, be admitted for overnight observation, and be evaluated by urology. Typically, the patient goes home with a Foley leg bag and undergoes urodynamic testing 1 to 2 weeks later after being discharged with medication for benign prostatic hypertrophy. The occurrence of urinary retention will not change the study intervention regimen or the schedule of participant assessments.

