9.1.5 Secondary outcomes and hypotheses

Again note that this pilot trial is not powered to detect differences in the secondary (clinical) outcomes described below. Our hypotheses reflect expected findings for a larger, multisite randomized clinical trial that will follow this pilot study.

- 1) Outcome: Quality of life
 - a. Hypothesis: quality of life will be significantly improved when older adults have their inguinal hernias repaired under local rather than general anesthesia.
- 2) Outcome: Physical function
- 3) Hypothesis: physical function (activities of daily living) will be significantly improved when older adults have their inguinal hernias repaired under local rather than general anesthesia.
- 4) Outcome: Cognitive function
 - a. Hypothesis: Cognitive function will be significantly improved when older adults have their inguinal hernias repaired under local rather than general anesthesia.
- 5) Outcome: Pain
 - a. Hypothesis: Pain will be similar for older adults having hernia surgery regardless of anesthesia modality.
- 6) Outcome: Postoperative complications
 - a. Hypothesis: The overall incidence of postoperative complications will be significantly reduced when older adults have their inguinal hernias repaired under local rather than general anesthesia. This will mostly be due to decreased rates of urinary retention (a common complication of general anesthesia).
- 7) Outcome: Operative and anesthesia times
 - a. Hypothesis: Time for surgery (incision to closure) and anesthesia (enter to exit operating room) will be significantly decreased when older adults have their inguinal hernias repaired under local rather than general anesthesia.
- 8) Outcome: Recovery time (time spent in the post-anesthesia care and stepdown units)
 - a. Hypothesis: Time spent in the post-anesthesia care and stepdown units after surgery will be significantly decreased when older adults have their inguinal hernias repaired under local rather than general anesthesia.

State the statistical hypotheses.

Describe the reasons for choice of study design (e.g., parallel groups, crossover, immediate versus deferred intervention, factorial, large simple trial, equivalency or non-inferiority trial); why certain design features were chosen (e.g., for a crossover trial, how the length of the washout period was chosen).

Describe the primary and secondary hypotheses and the primary and secondary outcome measures as well as their validity and reliability.

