- iv. Neuralgia/chronic pain: if patients experience pain at/near the site of surgery for >3 months after the operation, they are considered to have neuralgia. This will be managed initially by consultation with the pain service for injection of steroids and local anesthetic at the site for up to 3 times. If this proves unsuccessful, the patient will be considered for surgical neurectomy.
- v. Spermatic cord injury or orchitis: during surgical repair, the spermatic cord (including vas deferens, spermatic artery, venous plexus) are mobilized away from the hernia sac. If the surgeon identifies injury (division of the vas deferens, bleeding from artery or veins that requires intervention beyond holding pressure) or if there is involution of the testicle on the side of the surgery (identified by pain beyond the ordinary, swelling in the groin, ultrasound showing no flow) then we will categorize as a spermatic cord injury. Intraoperatively, a vas deferens injury will result in consultation of urology for repair. Arterial and venous injuries are generally too small to repair intraoperatively, but vascular surgery service can be consulted for evaluation. Postoperatively, there is no treatment for cord injury other than pain control, urologic evaluation, and possible removal of testicle on the injured side.
- vi. Urinary retention: per our standard hospital protocol, if patients are unable to urinate by four hours after surgery, we will perform a bladder scan. If >200 mL of urine is seen, the patient will receive an in-and-out catheterization followed by observation for up to an additional four hours. If the patient is still unable to urinate, they will have a Foley catheter placed, be admitted for overnight observation, and be evaluated by urology. Typically, the patient goes home with a Foley leg bag and undergoes urodynamic testing 1 to 2 weeks later after being discharged with medication for benign prostatic hypertrophy. The occurrence of urinary retention will not change the study intervention regimen or the schedule of participant assessments.

- vii. Reoperation: Any unplanned surgery after the participant leaves the operating room following repair of the hernia.
- viii. Unplanned readmission or emergency room visit: Any admission for a planned outpatient surgery, or any hospital admission or emergency room visit that occurs after discharge.

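### Section 6.2.3 gives no admission step for persistent urinary retention while sections 5.3.1, 7.1.5 and 9.4.2 admit the patient, so unplanned admission and step-down time depend on which text is followed

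*Combined protocol and SAP*

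**What the plan says.** Four places describe what happens to a patient with retention after surgery.

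- **Section 6.2.3, Visit 3 (urinary function).** The text presents itself as the standard: "Our standard clinical protocol is that if patients have not urinated by 4 hours after surgery, they will undergo a bladder scan". Above the volume threshold, the patient has in-and-out catheterization and is watched, with no stated limit, until the next void. If voiding fails, a Foley catheter is placed, prostate medication is started, and "arrangements are made with the urology service to undergo outpatient voiding studies and removal of the catheter within 1-2 weeks".
- **Section 5.3.1.** After in-and-out catheterization and up to 4 hours of observation, patients with continuing retention are handled as follows: "they will be admitted to the hospital with placement of a Foley catheter and subsequent evaluation by urology".
- **Section 7.1.5, repeated as section 9.4.2, item 5 vi.** This text also calls itself the standard hospital protocol. After up to four more hours, "they will have a Foley catheter placed, be admitted for overnight observation, and be evaluated by urology". Discharge with a leg bag and urodynamic testing 1 to 2 weeks later follow.

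Other sections attach consequences to an admission.

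- Unplanned admission has its own row in the schedule of evaluations (6.1). Section 9.4.2, item 5 viii counts "Any admission for a planned outpatient surgery" as a complication.
- Section 7.1.2 makes "inpatient hospitalization or prolongation of existing hospitalization" a criterion for a serious adverse event, and section 7.3.2 requires such events to be reported within 24 hours.
- Section 9.4.2, item 7 ends step-down time at hospital discharge, or, for admitted patients, at arrival in an inpatient or observation unit.

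Section 7.1.5 lists retention under the heading "SAE/AE occurring only with general anesthesia". Section 9.1.5 predicts fewer complications with local anesthesia and adds: "This will mostly be due to decreased rates of urinary retention".

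**The concern.** Two versions of the pathway are both labelled standard, and they part at the point where an admission either does or does not occur. Admission is itself a measured outcome, so the handling rule, and not only the anesthetic, helps determine the result.

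This matters in a pilot because its estimates are meant to be carried forward. Section 9.4.1, item 7 uses the observed proportions to size the multisite trial, and section 9.1.4 uses them to help choose its primary outcome. Section 2.2 already links unresolved retention to unplanned admission and hospital cost, so an admission outcome is a plausible candidate. An admission rate that mixes two handling rules would be hard to interpret for that purpose.

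The heading of section 7.1.5 raises a smaller, related problem. It assigns to one arm an event that the plan looks for in both.

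**Working it through.** The plan states no figure on this point, so there is nothing to reproduce. The check is a comparison of texts, followed by an illustration under stated assumptions.

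**Step 1. The texts side by side, for a patient still unable to void**

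| Section | Observation after in-and-out catheterization | Next step | Admission |
|---|---|---|---|
| 6.2.3, Visit 3 | until the next void, no limit given | Foley, medication, outpatient urology | not mentioned |
| 5.3.1 | up to 4 hours | Foley, urology evaluation | to the hospital |
| 7.1.5 | up to 4 further hours | Foley, urology evaluation | overnight observation |
| 9.4.2, item 5 vi | same text as 7.1.5 | same | same |

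No section says which text governs.

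**Step 2. Which outcomes depend on the text followed**

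- *Unplanned admission:* yes. Sections 5.3.1, 7.1.5 and 9.4.2 all use the language of admission. Section 6.2.3, read literally, produces none.
- *Step-down time:* yes. The observation limit differs, and so does the event that stops the clock (item 7 of 9.4.2). The direction of the change cannot be determined from the documents.
- *Serious adverse event:* yes under 5.3.1. Under 7.1.5 and 9.4.2 it depends on whether overnight observation is inpatient hospitalization. The documents do not say, and item 7 of 9.4.2 names inpatient and observation units as alternatives.
- *Count of urinary retention:* no. The patient has retention under every text.
- *Patient-level incidence of any complication:* no. Retention is already a listed complication, so the patient counts once with or without admission.

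**Step 3. Possible size**

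The documents give neither the retention rate nor the share of cases that persist. Assume:

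- n = 40 general-anesthesia patients (section 9.2.1)
- r = retention rate, 5% to 20% (assumed)
- s = share still unable to void after in-and-out catheterization, 25% to 100% (assumed)

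Expected admissions = n × r × s. Chance of at least one = 1 − (1 − r × s)^40.

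| r | s = 25% | s = 50% | s = 100% |
|---|---|---|---|
| 5% | 0.5 (0.395) | 1 (0.637) | 2 (0.871) |
| 10% | 1 (0.637) | 2 (0.871) | 4 (0.985) |
| 20% | 2 (0.871) | 4 (0.985) | 8 (above 0.99) |

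Each cell gives expected admissions in that arm under the admission texts, with the chance of at least one in parentheses. Under 6.2.3 read literally, every cell is 0. As a share of the arm, the range is 0.5/40 = 1.25% to 8/40 = 20%.

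**Step 4. The arm label**

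Under section 6.2.3, patients in the step-down unit are asked to void so that retention can be ruled out, and every local-anesthesia patient goes to that unit. Sections 5.3.1 and 9.4.2 set out retention without restricting it to an arm. Section 9.1.5 predicts a lower rate with local anesthesia, not a rate of zero. The heading of 7.1.5 conflicts with all of these.

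**The case against.** The best defense is that section 6.2.3 leaves admission out but does not exclude it. There, outpatient describes the voiding studies, and sections 7.1.5 and 9.4.2 place similar testing after the overnight stay. The Visit 3 text tells research assistants what to extract from nursing notes, and the next bullet covers unplanned admission. It could be a shortened account of the same pathway. This stands as a limit: no admission is the natural reading, not an explicit rule. It does not remove the conflict, because the text calls itself the standard protocol and also differs on observation time.

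Much of the needed data collection already exists. Catheterization and unplanned admission have separate rows in the schedule, retention and admission are separate items in 9.4.2, and 6.2.3 has staff find out the reason for any admission. This also stands. What is missing is a single pathway and a classification of overnight observation.

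The stakes are limited. The primary outcomes are feasibility measures, and section 9.1.3 calls the effect-size work exploratory.

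A reader might infer that the two sites will follow different texts and so bias the comparison. Nothing in the documents shows that the sites differ. Sections 3.5 and 9.2.1 stratify randomization by site (although the Précis says otherwise), so a site difference would fall on both arms. It could change the size of an admission difference but would not by itself favor an arm.

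**Conclusion.** The point holds as an internal inconsistency in operative text. Unplanned admission and step-down time depend on which section is followed. Serious-adverse-event status depends on it under 5.3.1, and under 7.1.5 and 9.4.2 only if overnight observation is treated as inpatient hospitalization. Under the assumed rates, about 0.5 to 8 expected general-arm admissions exist under one set of sections and none under the other. That range rests wholly on the two assumed inputs and on reading 6.2.3 literally.

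Three stronger readings are tempting but unsupported.

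- *Each retention case could add one, two or three adverse outcomes.* The plan defines no summed count. Section 9.4.2 codes complications as present, and section 9.5.2 compares proportions. The expectation in 9.1.5 that retention drives the difference concerns overall complication incidence, which at patient level does not change.
- *The pathway moves the admission difference by one definite amount.* For example, persistent retention in 4 of 40 general and 1 of 40 local patients would give 4/40 − 1/40 = 7.5 percentage points. That is a single assumed scenario.
- *All 4 + 1 = 5 of those patients would be serious adverse events.* That is clear only under 5.3.1.

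The heading of 7.1.5 is wrong on the plan's own terms. This is a labelling error: voiding is assessed in both arms, and no loss of data is shown.

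**What to change.** - Sections 5.3.1, 6.2.3 (Visit 3), 7.1.5 and 9.4.2 (item 5 vi) must be reconciled to one pathway, including the observation period, for use at both sites. Which pathway is right is a clinical matter on which this review takes no position.
- State whether overnight observation counts as an unplanned admission and whether it counts as a serious adverse event.
- Report unplanned admission with retention-related admissions identified, using the reason for admission that 6.2.3 already has staff obtain.
- Move urinary retention from section 7.1.5 to section 7.1.4, the list of events possible in either arm.

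The cost is protocol wording and one line in the analysis text. No new data are needed.
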